The efficacy and safety of internal defibrillation: evaluation of the iD-System[™], One-Handed Disposable Internal Defibrillation System

Protocol Version 1.0, 28 November 2017

NCT04011631

SUMMARY

Title	The efficacy and safety of internal defibrillation: evaluation of the iD-
	System [™] , One-Handed Disposable Internal Defibrillation System
Acronym	Internal defibrillation: iD-System™
Principal Investigator	[name]
Version & date	Version 1.0, 28 November 2017
Company	SMART Clinical Products
Study site	Ziekenhuis Oost-Limburg
Study period	February 2018-April 2018
Rationale	The iD-System [™] is designed for internal defibrillation in the same manner as the conventional internal paddles, which are used during intra-thoracic surgery. It delivers a shock to a patient's heart to restore normal sinus rhythm. The iD-System is a one-handed disposable medical device reducing the risk of cross contamination and the cost of sterilization. Moreover, it can be used in small-incision surgery due to its small size making it attractive for use in cardiac surgery.
Objectives	The main aim is to evaluate the safety and efficacy of the iD-System Safety: - To assess the ease of use of the device To assess passible complications
	 For assess possible complications Efficacy: To assess a successful restoration of the sinus rhythm
Investigational	The iD-System™ consist of two components:
material and	,
comparator products	1. The iD-Paddle [™] is a disposable sterile one-handed paddle. The iD-
	Paddle is placed in contact with the heart when needed to deliver
	a shock to restore normal sinus rhythm.
	2. The iD-Electrode [™] is a disposable non-sterile electrode pad placed
	on the back of the patient and connected to the same defibrillator
	as the iD-Paddle.
	Both the iD-Paddle ^{m} and the iD-Electrode ^{m} are connected with the
	defibrillator/monitor via the iD-SMART Cable. The iD-SMART Cable
	ensures that the Internal Joules Protocol will be initiated, with a
	maximum of 50 Joules. The iD-SMART Cable is specific for each type of
	defibrillator/monitor.
Number of subjects planned	100 patients with cardiac surgery, approximately 10% with need of internal defibrillation
Duration of study	2 months
Duration of study	5 11011015

Inclusion and	Inclusion criteria
exclusion criteria	 All races and ethnicity (>18 years) Written informed consent form (ICF) has to be obtained from the patient. Elective surgery: cardiac surgery on pump (CPB) Coronary artery bypass surgery Heart valve repair and/or replacement Mini sternotomy Median sternotomy Redo surgery
	 Exclusion criteria Patients without cardiopulmonary bypass (referred to as heart- lung machine or pump) Emergency surgery without a sufficient amount of time to explain and ask for ICF
Study design	Prospective interventional study with medical device

1. ETHICS

1.1. Independent Ethics Committee

The protocol and local Informed Consent Form must be reviewed and approved by the institution's Independent Ethics Committee (IEC) prior to the initiation of patient enrolment. The IEC will be notified of all subsequent protocol amendments. In addition, progress reports will be submitted to the IEC by the investigator as indicated by IEC's guidelines.

1.2. Ethical conduct of the study

The study will be conducted in accordance with the protocol, the principles that have their origins in the Declaration of Helsinki, as well as ICH GCP (Version 4, June 1996) and applicable national and local regulatory requirements, including but not limited to the Belgian Laws of 7 May 2004 relating to experiments on the human person (LEH), of 22 August 2002 on Patients' Rights and of 8 December 1992 (as amended) regarding the Protection of Privacy in relation to the Processing of Personal Data. All essential documents will be archived.

1.3. Patient information and informed consent

The informed consent will contain all elements required by ICH GCP. Written informed consent will be obtained from the patient prior to enrolment and participation of the study subject. The study centre further commits to conduct the study only on the basis of prior written consent by the subjects.

2. INVESTIGATORS AND STUDY ADMINISTRATION STRUCTURE

2.1. Investigators

Ziekenhuis Oost-Limburg will enroll approximately 100 patients. The trial will be supported by SMART Clinical Products by providing an internal defibrillation device and materials as specified above. SMART Clinical Products will be responsible for the technical support during the entire study period.

3. INTRODUCTION

In the majority of cardiac surgical interventions, cardiopulmonary bypass (CPB) is used because of the difficulty of operating on the beating heart. CPB is referred to as a heart-lung machine as the technique temporarily takes over the function of the heart (pump blood) and lungs (supply oxygen to red blood cells) during surgery (1). However, it is common for the post ischemic heart to fibrillate immediately after reperfusion and prior to weaning from extracorporeal circulation. This is referred to as ventricular fibrillation or tachycardia where cardiac electric shocks are often needed to restore the sinus rhythm of the heart (figure 1) (2,3). Therefore, intraoperative cardiac defibrillation is needed of which the most popular system consists of two spoon electrodes applied directly to the epicardium. The paddle handles are held by a surgeon when the electric current is passed from one spoon electrode through the patient's heart to a second spoon electrode (4). With the current tendency to reduce incision length in cardiac surgery, these paddles often turn out too bulky (5). Additionally, prior to use, the defibrillation handles and electrodes must be sterilized properly to eliminate patient infection. The handles have to be replaced after 25 cycles using steam sterilization or 100 cycles using hydrogen

peroxide gas sterilization (6). Independent of the sterilization, a defibrillation test has to be performed using a defibrillator analyzer after ten sterilization cycles or quarterly whichever comes first. The internal electrodes have to be replaced after 10 cycles using steam and 1 cycle using gas sterilization.

Figure 1: Normal and pathological electrocardiograms (ECG) related to internal fibrillation during cardiac surgery Recently, with this knowledge, studies have shown that systems using a single paddle and an external adhesive pad positioned at the patient's back reached the same reliability and function (5).

SMART Clinical Products developed a disposable device (iD-System[™], One-handed Disposable Internal Defibrillation System; figure 2) consisting of a single paddle (iD-Paddle) designed with a flexible head to maximize the contact with the heart. The adhesive pad (iD-Electrode), positioned at the patient's back, serves as a positive pole to guarantee an electric circuit transferred from a defibrillation device to the patient's heart. The iD-Sytem[™] is connected to the defibrillator/monitor, via a specific iD-SMART Cable. More information about the product, the company and their strategy is provided in the evaluation plan (attachment 1) and the brochure (attachment 2).

Figure 2: the iD-SystemTM developed by SMART Clinical Products consisting of the iD-Paddle, the iD-Electrode and the iD-SMART Cable.

In UZLeuven, this device was tested and the following conclusions were made in comparison to the conventional system (5)

- it can easily be used as a hybrid (both external and internal cardioversion) system
- it consists of disposable materials (reducing the risk of cross contamination and the cost of sterilization process). The iD-SMART Cable is a reusable product. The iD-SMART Cable will not be in direct contact with the patients tissue.

- its small size and single contact point approach permits safe use in limited access conditions such as with small-incision surgery and in redo surgery associated with extensive adhesions.

Since it is the current that defibrillates, impedance or resistance is important. With constant energy selected on the defibrillator device, defibrillation effectiveness is related to the resistance between the defibrillator and the patient's heart (7). The lower the resistance or impedance, the higher the defibrillation success. Myocardial injury associated with defibrillation corresponds not only with total joules used (energy), but also with the time interval between the defibrillation shocks. Therefore, throughout the cardiac surgery, perioperative myocardial damage is measured by electrocardiogram (ECG) and by cardiac troponin levels. Troponin levels indicate the severity of cardiac damage(8).

4. OBJECTIVES

The main aim is to evaluate the safety and efficacy of the iD-System[™], One-handed Disposable Internal Defibrillation System The device is made for manual defibrillation during intra-thoracic procedure, by transferring a shock from a defibrillation device to the patient's heart, in combination with the iD-Electrode. The device will be used when the patient reaches a stage of ventricular fibrillation or rapid ventricular tachycardia during cardiac surgery.

- Safety:
 - To assess the ease of use of the device:
 - Adherence of the iD-Electrode to the patient's back
 - Positioning of the iD-Paddle for maximal contact with the heart
 - Working length of the following cables: iD-Electrode, iD-Paddle and the iD-SMART Cable
 - Applicability in small-incision surgery: mini sternotomy
 - To assess possible complications:
 - Skin symptoms to the electrode
 - Myocardial injury: troponin measurement
- Efficacy
 - To assess a successful restoration of the sinus rhythm
 - Number of failed attempts to defibrillate which were attributable to device malfunction.

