5. INVESTIGATIONAL PLAN

5.1. **Patient population**

All patients undergoing cardiac surgery, meeting all inclusion and no exclusion criteria, are asked to participate.

- 5.2.1. Inclusion criteria
 - All races and ethnicity (>18 years)
 - Written informed consent form (ICF) has to be obtained from the patient.
 - Elective surgery: cardiac surgery on pump (CPB)
 - Coronary artery bypass surgery
 - Heart valve repair and/or replacement
 - Mini sternotomy
 - Median sternotomy
 - Redo surgery

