5.2. Study design

The iD-System[™], One-handed Disposable Internal Defibrillation System is already tested by the biotechnical department of Ziekenhuis Oost Limburg (ZOL) which ensured proper working between the iD-System and the used defibrillator/monitor in ZOL (LIFEPAK[®] 20) (attachment 3 and attachment 3.1). In every included patient undergoing cardiac surgery on CPB/pump (during February 1st 2018 until April 30rd 2018), the iD-Electrode is placed prophylactically on the patient's back and is connected to the defibrillator in case ventricular fibrillation would occur. In every patient, the usability of the iD-System is determined according to a questionnaire focused on safety (figure 1: step 1-4, step 6). The questionnaire is available in attachment 4.

Figure 3: Instructions for use of the iD-System.

When ventricular fibrillation of ventricular tachycardia occurs, the iD-Paddle will be applied directly to the heart. (figure 1: step 1-10)

The surgeon selects the right amount of Joules, with a maximum of 50 Joules, conform to the defibrillator 'LIFEPAK 20®'. The device may only be used by medical specialist and nurses, in the operating area. In case of internal defibrillation, extra questions (attachment 4) focused on efficacy will be filled in by the surgeon. We hypothesize that in 10% of the study population, thus 10 patients (out of 100), ventricular fibrillation or tachycardia will occur. In this small subpopulation, the ease of use of the iD-Paddle and the efficacy can be tested. In case that this number is not reached, the ease of use of the iD-Paddle can be tested without defibrillating the patient. We will then connect the iD-Paddle to the iD-Cable and press the iD-Paddle on the heart without pressing the 'charge' and 'shock' button.

In case ventricular fibrillation occurs and the iD-System is not effective to restore the sinus rhythm, the conventional approach with use of the two paddles spoons will be performed. One paddle is placed behind the left ventricle, and the other is positioned over the right ventricle on the anterior surface of the heart, with current flowing directly through the heart.

During surgery, all patients are monitored to observe possible abnormalities on ECG. As part of standard of care, blood samples are taken at certain time points to measure myocardial damage (troponin-T).

The suspected workflow is the following:

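### Efficacy is judged by restored sinus rhythm, so, read literally, a shock that ends VF/VT in a patient with a pre-existing non-sinus rhythm counts as unsuccessful

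*Combined protocol and SAP*

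**What the plan says.** Section 4 (Objectives) has two efficacy items. The first is the success outcome: "To assess a successful restoration of the sinus rhythm". The second is a count of failures from one cause: "Number of failed attempts to defibrillate which were attributable to device malfunction". The Summary lists only the first. No time point, unit of scoring or denominator is given for either.

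The indication is also in Section 4: "The device will be used when the patient reaches a stage of ventricular fibrillation or rapid ventricular tachycardia during cardiac surgery".

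On who enters the study, Section 5.1 says: "All patients undergoing cardiac surgery, meeting all inclusion and no exclusion criteria, are asked to participate". The criteria, in the Summary and in 5.2.1 and 5.2.2, cover age, consent, elective on-pump surgery, and type of operation or access, including valve and redo surgery. None mentions pre-operative rhythm.

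On numbers, Section 5.2 (Study design) says: "We hypothesize that in 10% of the study population, thus 10 patients (out of 100), ventricular fibrillation or tachycardia will occur". It then provides for a shortfall: "In case that this number is not reached, the ease of use of the iD-Paddle can be tested without defibrillating the patient".

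Efficacy data come from surgeon questions in Attachment 4, and the defibrillation pathway is in Figure 4. Section 7 plans a description of the patient population and no in-depth analysis.

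**The concern.** The outcome and the indication are different things. The device is called on to end VF or rapid VT. The stated success is a particular rhythm afterwards. The two agree in a patient who was in sinus rhythm before surgery and returns to it. They can part in a patient whose usual rhythm is not sinus, for example atrial fibrillation or a paced rhythm. There the shock may end VF/VT and the usual rhythm may return. The shock has then done what it was given for, but the Section 4 wording, taken at face value, records no success.

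What is at stake is how the efficacy result is read. Efficacy is half of the study's main aim, and it rests on the small group who are shocked. If fewer than 10 events occur, the fallback adds ease-of-use data from paddle contact without a shock. It adds nothing on efficacy, so each doubtful case weighs more. The error runs in one direction only, against the device.

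**Working it through.** **The plan's own figure.** Section 5.2 gives 100 patients and a 10% event rate: 100 × 0.10 = 10 shocked patients. This reproduces. The documents contain no other sample-size or power calculation.

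**Can the case arise?** Three statements taken together say yes:
- Use of the device is triggered by VF or rapid VT (Section 4).
- Success is sinus rhythm (Section 4 and Summary).
- No inclusion or exclusion criterion concerns rhythm (Summary, 5.2.1, 5.2.2).

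The second efficacy item does not close the gap. It counts failures put down to device malfunction, and a shock that ended VF/VT need not enter that count. No part of the available text makes termination of VF/VT an outcome.

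**Weight of one case.** The plan defines no efficacy proportion, so the measure here is an illustration: patients with success divided by patients shocked (N). One reclassified patient moves it by 1/N. Suppose every shock in fact ends VF/VT. Intervals are Clopper-Pearson 95%. For N/N the lower limit is 0.025^(1/N). For (N−1)/N the upper limit is 0.975^(1/N), and the lower limit is the 2.5% point of a Beta(N−1, 2) distribution.

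At N = 10:
- no such case: 10/10 = 100%; 0.025^(1/10) = 0.692, so 69.2-100%
- one case: 9/10 = 90% (55.5-99.75%)
- two cases: 8/10 = 80% (44.4-97.5%)
- three cases: 7/10 = 70% (34.8-93.3%)

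**If the number shocked is not 10.** Assume each of 100 patients independently has the plan's 10% chance. Under Binomial(100, 0.10), the number shocked is 5 to 16 with probability 95.6%, and below 10 with probability 45%.
- N = 5: one case moves the result by 1/5 = 20 points, from 5/5 (47.8-100%) to 4/5 (28.4-99.5%).
- N = 16: one case moves it by 1/16 = 6.25 points, from 16/16 (79.4-100%) to 15/16 (69.8-99.8%).

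**How likely is at least one case?** The documents give no share of patients with a non-sinus rhythm. As a pure assumption, let a share q of 10 shocked patients have one. The chance of at least one is 1 − (1 − q)^10:
- q = 5%: 40%, expected number 0.5
- q = 10%: 65%, expected number 1
- q = 20%: 89%, expected number 2
- q = 30%: 97%, expected number 3

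These chances show sensitivity to q and are not estimates for this hospital. They also count patients at risk of being mis-scored, which is an upper bound on the number actually mis-scored.

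**The case against.** The strongest reply is that the phrase is shorthand. The Summary says of the device: "It delivers a shock to a patient's heart to restore normal sinus rhythm". The Introduction says that "cardiac electric shocks are often needed to restore the sinus rhythm of the heart". Both use sinus rhythm as the general aim of a shock for VF/VT. The Introduction also speaks of defibrillation success, and the second efficacy item frames failure as failed defibrillation. On that reading nothing is misclassified. This is plausible, and no available text tells the surgeon to score literally. But no available text states the shorthand either, and the Section 4 line is what a report would be held to.

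A second reply is that the answer may lie in material not available here: the Attachment 4 questions, the Figure 4 flow chart, the evaluation plan in Attachment 1, or the patient characteristics and surgery report collected for every patient. This stands as a limit. A reader might infer that the plan has no usable definition of success. The documents do not support that, because the form that captures efficacy cannot be inspected.

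A third reply is that no planned result changes. Section 7 sets no success proportion, interval or decision rule, and the 1/N effect holds for any misclassified patient in a group this small. Both points are right, and they keep the priority low. They do not make the outcome match the indication.

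A reader might also infer that the move to the conventional paddles in Section 5.2 is at fault, because it uses the same sinus-rhythm wording. The documents show shared wording there and no demonstrated contradiction.

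**Conclusion.** The point holds as an improvement that could be made, with medium confidence. The success outcome in Section 4, applied as written, can score a shock that ended VF/VT as unsuccessful when the patient's earlier non-sinus rhythm returns, and the eligibility criteria admit such patients. At the expected 10 shocked patients each case costs 10 percentage points, or 20 to 6.25 points across 5 to 16 shocked patients. The intervals overlap widely.

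This rests on three assumptions: that the wording is scored literally, that a simple per-patient proportion is reported, and that at least one such case occurs. A reader might go further and conclude that the efficacy result will be biased. The documents do not support that, since they give no share of non-sinus rhythm and the number of affected patients may be zero. Nor is any test or decision at risk, since none is planned.

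**What to change.** In Section 4, make the efficacy measure *termination of VF/VT by the iD-System before any use of the conventional paddles*. Report it as n/N, where N is all patients given at least one iD-System shock. Patients in whom the paddle only touches the heart without a shock are not in N. Keep *sinus rhythm restored* as a separate outcome. List pre-operative and post-shock rhythm for each shocked patient; with about 10 rows, a listing serves better than rhythm subgroups.

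If the attachments already record these items, only the Section 4 line is needed. Otherwise the cost is two rhythm fields on the form. Patients are already ECG-monitored during surgery (Section 5.2), so no procedure is added, although the rhythm must be written down. The downside is two efficacy results to report and explain.

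Because Section 5.2 uses the same sinus-rhythm wording, the investigators should check that it remains consistent with Section 4 once the outcome is changed. No clinical rule is proposed.

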5.2.2. Exclusion criteria

- Patients <18 years
- Patients without cardiopulmonary bypass (referred to as heart-lung machine or pump)
- Emergency surgery without a sufficient amount of time to explain and ask for ICF

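### Section 4 counts failed attempts only when the device malfunctioned, so on a per-patient reading one-shock and multi-shock restoration give the same efficacy result

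*Combined protocol and SAP*

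**What the plan says.** Section 4 (Objectives) gives two items under efficacy. One is "To assess a successful restoration of the sinus rhythm". The other is "Number of failed attempts to defibrillate which were attributable to device malfunction". The summary at the front of the protocol lists only the first. Neither place says whether restoration is scored per patient, per episode or per shock.

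Section 3 (Introduction) explains why a shock may or may not work: "The lower the resistance or impedance, the higher the defibrillation success". It adds that myocardial injury "corresponds not only with total joules used (energy), but also with the time interval between the defibrillation shocks". Section 4 lists troponin as a safety measure of that injury.

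Section 5.2 (Study design) sets the size of the efficacy group: "We hypothesize that in 10% of the study population, thus 10 patients (out of 100), ventricular fibrillation or tachycardia will occur". It says that the conventional two-paddle approach follows if the iD-System does not work, and it sends the efficacy questions to Attachment 4. Section 7 (Statistical analysis) commits to describing the patient population and adds no efficacy measure.

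**The concern.** The only failed-attempt count in the visible text is filtered by cause. On the protocol's own account of impedance, a shock can fail while every component works, for example because paddle contact is poor. For a single paddle paired with a back electrode, that kind of failure is of direct interest. The malfunction filter removes it from the second item. If a later iD-System shock then works, a per-patient reading of the first item removes it there too.

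Efficacy is half of the main aim and rests on about 10 patients. A device that works at once and a device that needs repeated shocks could be reported identically. Troponin would also be presented without the energy and shock information that Section 3 says it depends on.

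**Working it through.** **Inputs.** From Section 5.2: 100 patients and a 10% rate of ventricular fibrillation or tachycardia. From Section 4: the two efficacy items. Assumed, because the documents give no figures: the number of patients needing an extra shock, and the success rate per shock.

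**The plan's own figure.** 100 × 0.10 = 10 patients, which reproduces. If 10% is the true rate, the binomial 95% range is 5 to 16 patients.

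**Where each kind of failed shock is counted, reading restoration per patient:**

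| What happens | Restoration item | Failed-attempt item |
|---|---|---|
| Malfunction, then a successful iD-System shock | restored | counted |
| Failure without malfunction, then conventional paddles | not restored by the iD-System (implied by Section 5.2) | not counted |
| Failure without malfunction, then a successful iD-System shock | restored | not counted |

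Only the third row leaves no trace of the failed shock in either item.

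**Size of the effect.** Assume 10 patients, all restored by the iD-System, no malfunction, and m of them needing exactly one extra shock. Then failed shocks = m, total shocks = 10 + m, and first-shock restoration = (10 − m)/10. The exact (Clopper-Pearson) limits for x of n are the 2.5% point of Beta(x, n − x + 1) and the 97.5% point of Beta(x + 1, n − x). For 10/10 the lower limit is 0.025^(1/10) = 0.692 and the upper limit is 1.

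| m | Restored (95% CI) | Malfunction failures | Failed shocks / all shocks | Restored by first shock (95% CI) |
|---|---|---|---|---|
| 1 | 10/10 (69.2–100%) | 0 | 1/11 | 9/10 (55.5–99.7%) |
| 3 | 10/10 (69.2–100%) | 0 | 3/13 | 7/10 (34.8–93.3%) |
| 5 | 10/10 (69.2–100%) | 0 | 5/15 | 5/10 (18.7–81.3%) |

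The second and third columns, which are the stated outcomes, do not change.

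**How likely the situation is.** With a constant success probability p per shock, the chance that at least one of 10 patients needs more than one shock is 1 − p^10. For assumed p = 0.9, 0.7 and 0.5 this gives 65%, 97% and 99.9%.

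**Dependence on the reading.** If restoration were scored per shock instead, the failed shocks would show as non-successes: 10/11 = 90.9%, 10/13 = 76.9% and 10/15 = 66.7%. The loss of information therefore depends on the per-patient (or per-episode) reading.

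**The case against.** The strongest reply is that the unit of restoration is undefined. The second item counts attempts, so the first could be scored per attempt as well, and then nothing is lost. That stands as a limit on the finding. Per patient is the more natural reading, but the text does not choose, and the choice should not be left until the data are in.

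A reader might infer that the Section 4 bullets are the only statement of what efficacy results will be reported, or that shock number and energy will not be collected. The documents do not support either inference. The clinical evaluation plan (Attachment 1), the questionnaire (Attachment 4) and the Figure 4 flow chart were not in the text available, and any of them may cover these items. The finding is that the visible text names no such outcome.

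A reader might also take the Introduction's remark that "cardiac electric shocks are often needed to restore the sinus rhythm of the heart" as foreseeing repeated shocks in one patient. It more naturally says that defibrillation is often required across patients. The reference in the same section to the interval between shocks is the better support.

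Section 4 does assess paddle positioning for contact and electrode adherence under ease of use. That addresses one mechanism of failure but does not count failed shocks.

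Finally, the study has no comparator, success threshold or test. That is correct, and it limits the consequence to reporting. In a descriptive study, however, the listed outcomes are the result.

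**Conclusion.** The point holds for the outcomes as Section 4 states them, on a per-patient reading. A failed iD-System shock not due to malfunction, followed by a successful one, appears in neither efficacy item. Under the illustrative assumption, the report would read 10/10 and 0 whether first-shock restoration was 9/10, 7/10 or 5/10. The extra-shock numbers and per-shock success rates are assumptions.

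It would go too far to say that the restoration rate itself is wrong. No patient is reclassified, and 10/10 stays 10/10; what is missing is the number of shocks it took. How to score a return to a pre-existing non-sinus rhythm is a separate question of definition. The documents give no share of such patients, and the point here does not need it.

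The wording should be fixed, but the gap does not invalidate the study.

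**What to change.** In Sections 4 and 7:

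1. State that restoration is scored per patient, among all patients with ventricular fibrillation or tachycardia in whom iD-System defibrillation was attempted.
2. Report all failed iD-System attempts, with device malfunction as a sub-category.
3. Report, per patient, the number of shocks, total joules and whether the first shock restored rhythm, and show the shock and energy figures beside troponin.
4. In the analysis only, count a switch to the conventional paddles as an iD-System failure, as Section 5.2 already implies. The rescue step itself is unchanged.

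Check that Attachment 4 captures shock number, energy and rescue use, and add items only if it does not.

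The cost is wording and perhaps a few questionnaire items, with no extra patient or procedure. The downsides are slightly more recording for the surgeon and an efficacy picture that may look less favourable.
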